All clusters will begin the study in Group A and switch over to Group B at either 2, 4 or 6 months from when the first patient per cluster enters the PRIMETIME Information Giving Study. Group A will be given Version A of the PRIMETIME main study patient information sheet. Group B will be given Version B of the PRIMETIME main study patient information sheet. The description of the PRIMETIME Information Giving Study will differ between Version A and B with Version B specifying that patients will be provided with a video. This will be the only difference between Version A and B of the PRIMETIME main study patient information sheet.

Please Note – sites should not make patients aware of the availability of the video before the switch over date.

Group A

In Group A clusters, participants will have a discussion with a healthcare professional and be

provided with Version A of the PRIMETIME main study patient information sheet. After the

patient has made their decision regarding entry into PRIMETIME, they will be presented with

Questionnaire A which includes baseline demographics, questions regarding the information

provided and the decisional conflict questionnaire [1]. Return of the Questionnaire indicates

consent to the PRIMETIME Information Giving Study.

Group B

In Group B clusters, participants will have a discussion with a healthcare professional and be

provided with Version B of the PRIMETIME main study patient information sheet and given

access to the decision aid video. The video must be viewed after the consultation with the

healthcare professional and after the patient has read the PRIMETIME main study patient

information sheet. The video must also be viewed prior to the patient making their decision

regarding entry into the PRIMETIME main study. After the patient has made their decision

regarding entry into PRIMETIME, they will be presented with Questionnaire B which includes

baseline demographics, questions regarding the information provided and the decisional

conflict questionnaire [1]. Return of the Questionnaire indicates consent to the PRIMETIME

Information Giving Study.

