# **STATISTICAL CONSIDERATIONS**

Statistical design and sample size justification

The target sample size for the PRIMETIME Information Giving Study is 264 patients. This sample size is based on three steps in the cluster stepped-wedge trial design (at 2, 4 and 6 months) of 33 clusters (11 per step), with 2 patients per cluster per 2 month period. There is limited literature on what is a clinically significant reduction in decisional conflict. Two small single centre studies conducted in similar populations to patients in PRIMETIME found effect sizes around 0.40, with standard deviations for the total Decisional Conflict Scale score ranging from 11-25 [4,5]. As this is a cluster randomised trial, the sample size estimation needs to allow for possible clustering effects. However there is no data available on likely values of the intraclass correlation (ICC) for the Decisional Conflict Scale, and so estimates have been calculated across the range of ICC values from 0 to 1. Assuming an alpha of 0.05, 264 patients from 33 clusters would have at least 80% power for all values of the ICC to detect a 10-point difference in total score for the Decisional Conflict Scale (effect size=0.55, assuming standard deviation=18). If this target is not achievable, then 240 patients from 30 centres would provide at least 80% power to detect an effect size of 0.55 across most of the range of ICC values. The figure below illustrates the power for different scenarios according to value of ICC and number of clusters (with total number of patients also shown).

[figure not shown]

Figure 2: Power when intraclass correlation is varied

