**STATISTICAL ANALYSIS PLAN** 

The data will be analysed on the intention to treat (ITT) analysis set. According to the

intention to treat principle, clusters will be analysed according to randomised decision aid

video start time regardless of when the cluster started using the decision aid video [9].

Primary endpoint

Only patients who return questionnaires (i.e. consent to the PRIMETIME Information Giving

Study) will be analysed, regardless of whether they consent to participate in the PRIMETIME

main study.

The mean decisional conflict score pre- and post-implementation of the decision aid video

will be calculated (with 95% confidence interval). Calendar time is a possible confounder and

therefore any effect seen could be (partly or in full) due to underlying temporal trend [9]. To

adjust for calendar time and clustering the methods detailed in Hussey and Hughes [10] will

be followed, where a linear mixed model will be fitted with a random effect for cluster and a

fixed effect for each step.

A sensitivity analysis will be performed to compare the decisional conflict of those who

stated they watched the decision aid video (in Questionnaire B) compared to those who

stated they did not watch the decision aid video (in Questionnaire B) and those who were

not in a cluster using the decision aid video (i.e. were given Questionnaire A to complete).

Secondary endpoints

Acceptance of PRIMETIME main study entry - all participants who were given information

and were eligible to enter the PRIMETIME main study will be analysed. This follows an ITT

analysis where patients will be analysed according to the information (PRIMETIME main

study information sheet versus PRIMETIME main study information sheet and decision aid

video) their cluster was assigned to at that step. Therefore patients will be included

regardless of whether they returned a questionnaire.

A sensitivity analysis will be performed to compare the acceptance of PRIMETIME main

study entry in patients who stated they watched the decision aid video (in Questionnaire B)

compared to those who stated they did not watch the decision aid video (in Questionnaire

B) in addition to those who were not in a cluster using the decision aid video (i.e. were given

Questionnaire A to complete).

Acceptance of recommended treatment in patients consenting to the PRIMETIME main study

- all participants who were recruited into the main PRIMETIME main study will be analysed.

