This follows an ITT analysis where patients will be analysed according to the information

(PRIMETIME main study information sheet versus PRIMETIME main study information sheet

and decision aid video) their cluster was assigned to at that step. Therefore patients will be

included regardless of whether they returned a questionnaire.

A sensitivity analysis will be performed to compare the acceptance of recommended

treatment in patients consenting to the PRIMETIME main study in patients who stated they

watched the decision aid video (in Questionnaire B) compared to those who stated they did

not watch the decision aid video (in Questionnaire B) in addition to those who were not in a

cluster using the decision aid video (i.e. were given Questionnaire A to complete).

Both secondary endpoints will be analysed using a logistic regression model with a cluster

level fixed effect for assigned group at that step (PRIMETIME main study information sheet

versus PRIMETIME main study information sheet and decision aid video), with a random

effect for cluster and a fixed effect for each step [9, 10].

An interim analysis to review emerging data is planned in the first quarter of 2019 and will

include the facility to include data in a confidential PhD thesis. The final analysis will take

place once all the clusters have received the decision aid.

Data acquisition – Questionnaires will be completed at each centre by the patient and then posted back to the ICR-CTSU for data entry onto the PRIMETIME Information Giving Study database.

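### Minor improvement: the primary decisional-conflict model in Appendix A5 names no patient-level covariate, although both questionnaires collect baseline demographics and only women who return one are analysed

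*Protocol*

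**What the plan says.** Appendix A5 is the protocol of the Information Giving Study and has its own Statistical Analysis Plan section. For the primary endpoint it states that to "adjust for calendar time and clustering the methods detailed in Hussey and Hughes [10] will" be followed, and that "a linear mixed model will be fitted with a random effect for cluster" and a fixed effect for each step. The term for the video is not written out there. It is written out for the two secondary endpoints, whose logistic model has a cluster "level fixed effect for assigned group at that step (PRIMETIME main study information sheet" against sheet plus video). No patient characteristic appears in either model.

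The same section limits the primary analysis: "Only patients who return questionnaires (i.e. consent to the PRIMETIME Information Giving" Study) enter it, whether or not they join the main study. Both secondary endpoints include women regardless of return.

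The Study Design section describes "Questionnaire A which includes baseline demographics, questions regarding the information" provided and the decisional conflict questionnaire. Group B is described in the same way: once the woman has decided "regarding entry into PRIMETIME, they will be presented with Questionnaire B which includes" the same three components. The individual demographic items are not listed.

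**The concern.** Clusters, not women, are randomised, and what is randomised is the date of the switch to the video. A woman in Group B knows about the video, because Version B of the information sheet mentions it and she is given access to it. She decides about returning the questionnaire after that exposure, and return is itself consent to the sub-study. The mix of women who respond could therefore change when a cluster switches.

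The random cluster effect deals with stable differences between clusters, and the step effects deal with trends common to all clusters. Neither deals with a change in responders that accompanies the video. If such a change occurred in a characteristic related to decisional conflict, part of the estimated effect would be a difference in who answered. Demographics that predict the score could also reduce residual variance. The data for both purposes are already collected.

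**Working it through.** **Inputs from Appendix A5, Statistical Considerations.** The design has "three steps in the cluster stepped-wedge trial design (at 2, 4 and 6 months"), hence 4 periods, and "33 clusters (11 per step), with 2 patients per cluster per 2 month period". The difference is 10 points, the SD 18 (effect size 10/18 = 0.556, stated as 0.55) and alpha 0.05. The protocol does not say whether alpha is one- or two-sided; two-sided is assumed. The intraclass correlation (ICC) ranges from 0 to 1. Sample size: 33 × 4 × 2 = 264, as stated.

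**Formula.** Hussey and Hughes variance of the video effect, with *I* clusters, *T* periods, s² = within-cluster variance / 2 and τ² = between-cluster variance:

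Var = I·s²·(s² + T·τ²) / [(I·U − W)·s² + (U² + I·T·U − T·W − I·V)·τ²]

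Power = Φ(10/SE − 1.96)

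With 11 clusters in each of the patterns 0111, 0011 and 0001:

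- U = 11 × (3 + 2 + 1) = 66
- W = 0² + 11² + 22² + 33² = 1694
- V = 11 × (9 + 4 + 1) = 154
- I·U − W = 2178 − 1694 = 484
- U² + I·T·U − T·W − I·V = 4356 + 8712 − 6776 − 5082 = 1210

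**The plan's own figure, without covariates.**

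| ICC | SE | Power, 33 clusters |
|---|---|---|
| 0 | 3.32 | 85.3% |
| 0.05 | 3.44 | 82.9% |
| 0.10 | 3.47 | 82.1% |
| 0.12 (minimum) | 3.48 | 82.0% |
| 0.30 | 3.30 | 85.8% |
| 0.50 | 2.88 | 93.5% |

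At ICC 0.12, s² = 324 × 0.88 / 2 = 142.56 and τ² = 324 × 0.12 = 38.88. Then Var = 33 × 142.56 × 298.08 / (484 × 142.56 + 1210 × 38.88) = 12.08 and SE = 3.48. The claim of at least 80% power at every ICC is reproduced.

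For the fallback of 30 clusters (30 × 4 × 2 = 240 women) the variance is multiplied by 33/30. The minimum is 78.3%, and power is below 80% for ICCs of roughly 0.03 to 0.22. This agrees with the protocol's own statement that 80% holds over most of the range.

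**Possible gain in precision.** Multiply the within-cluster variance by (1 − R²), where R² is the share explained by demographics. The protocol gives no value, so R² is assumed.

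| Assumed R² | Minimum power, 33 clusters | Fall in SE at ICC 0.05 |
|---|---|---|
| 0 | 82.0% | – |
| 0.02 | 82.7% | 0.9% |
| 0.05 | 83.7% | 2.3% |
| 0.10 | 85.4% | 4.7% |

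For example, with R² = 0.10 at ICC 0.12, s² = 142.56 × 0.90 = 128.30, Var = 11.01, SE = 3.32 and power is 85.4%.

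**Possible shift from responder mix.** Shift = difference in the share of a binary characteristic between groups × its worth on the scale. Both inputs are assumed.

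- 0.05 × 2 points = 0.1 point
- 0.10 × 5 points = 0.5 point
- 0.20 × 5 points = 1.0 point
- 0.20 × 10 points = 2.0 points

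These compare with a target of 10 points and an SE of 3.3 to 3.5 at ICCs of 0 to 0.3.

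**The case against.** The strongest case against raising this is that nothing in the plan is wrong. The model follows the method that the protocol cites, it is a standard analysis of a stepped wedge, and it delivers the stated power without covariates. All of that stands.

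A reader might infer that the plan ignores demographics. The text does not support this: it names none, but it does not exclude them. It also leaves the video term implicit, so it reads as a summary of the model. Covariate lists are often settled in a separate statistical analysis plan. Against that, the deferral to such a plan closes section 12.4 on the main study, whereas Appendix A5 states its own model terms and contains no deferral. A suggestion about those stated terms is therefore fair, provided it is put as a suggestion.

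A reader might also infer that precision is lost or that power is under threat. At most a gain is forgone, and its size is unknown; at R² = 0.02 it is 0.7 percentage points of minimum power. The shortfall with 30 clusters is something the protocol itself discloses for a fallback.

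Finally, a reader might infer that the primary estimate is biased and that adjustment would cure it. Nothing in the protocol shows that return differs by group. The demographics come from returned questionnaires, so they say nothing about women who do not respond. Return driven by the participation decision, by decisional conflict or by the video itself would remain in the estimate after adjustment. This objection stands and limits what the change can achieve.

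**Conclusion.** The point holds as a minor, nearly free improvement and not as an error. The primary model names cluster and step effects, with video implied, and no patient-level covariate. Demographics are collected in both groups, and the analysis set is formed by a response given after exposure.

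The unadjusted analysis is valid and has a minimum power of 82.0% with 33 clusters. If demographics explain 2% to 10% of within-cluster variance, the minimum becomes 82.7% to 85.4%. The illustrated shift from responder mix is 0.1 to 2.0 points, and adjustment removes only the part explained by the recorded items. These gains rest on assumed values of R², of the difference in mix and of the worth of the characteristic, none of which the protocol supplies. The power figures also assume a two-sided test and the normal approximation.

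**What to change.** In the primary endpoint paragraph of the Appendix A5 analysis plan, name a small set of baseline demographics recorded in both questionnaires as patient-level fixed effects in the linear mixed model. Choose them from the questionnaires themselves, since the protocol does not list the items, and exclude any answer that the video could affect. State a simple rule for missing items. Report the unadjusted model alongside, and give questionnaire return rates by group, so that a reader can judge how much differential response is possible.

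Fix the list before outcome data are reviewed. The appendix plans an interim look at emerging data in the first quarter of 2019, so the list should precede that.

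The cost is a change of wording, a few degrees of freedom out of 264 women, and the handling of missing items. No further data or patients are needed.

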### Design of the PRIMETIME Information Giving Study

We propose to introduce a decision aid (in video format) in addition to written patient information, in order to optimise the decision making process for patients who are considering participating in PRIMETIME. The study will investigate the effect of the decision aid on patients' decisional conflict regarding their decision of whether or not to participate in the PRIMETIME main study.

We plan to use a 'study within a trial' approach or 'SWAT' as this can assess different ways of designing, conducting, analysing and evaluating studies through the conduct of research within research [6]. A cluster stepped-wedge trial design will be used for the PRIMETIME Information Giving Study. A cluster stepped-wedge trial consists of the sequential implementation of an intervention (the decision aid video) to participants (or in the case hospital sites) grouped within clusters over a number of time periods [7]. An example of a cluster is a group of hospitals under one National Health Service trust. All clusters will receive the intervention by the end of the study however the order in which clusters initiate the intervention is determined at random [7]. In general, cluster stepped-wedge trials are designed to study the effects of a new intervention implemented at cluster level, but which is experienced and measured at the individual patient level [8]. The justification for

implementing the decision aid video at cluster level is to ensure all patients being treated at

a study centre will receive the same information (either written patient information or

written patient information in conjunction with video) over pre-specified time periods. If the

decision aid was implemented at individual patient level then patients in a centre may

discuss the different formats of information they are receiving. This may compromise the

interpretation of decisional conflict.

We hypothesise that the decision aid video in addition to written patient information will

reduce decisional conflict and the stepped-wedge trial design ensures that by the end of the

PRIMETIME Information Giving Study all clusters will have used the decision aid.

Furthermore, in a cluster stepped-wedge trial each cluster acts as its own control, increasing

the statistical power of the study.

If the PRIMETIME Information Giving Study demonstrates that the introduction of a decision

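### The Information Giving Study's final analysis is triggered by the last cluster's switch, not by the 264 questionnaires or the fourth two-month period that the sample size needs

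*Protocol*

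**What the plan says.** All places are in Protocol Appendix A5.

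- **Trigger** (Statistical Analysis Plan): "The final analysis will take place once all the clusters have received the decision aid".
- **Target** (Statistical Considerations): "The target sample size for the PRIMETIME Information Giving Study is 264 patients". The design behind it is given as follows: "three steps in the cluster stepped-wedge trial design (at 2, 4 and 6 months) of 33 clusters (11 per step), with 2 patients per cluster". That rate applies to each two-month period. A fallback of 240 patients from 30 centres is also given.
- **Power** (same section): "Assuming an alpha of 0.05, 264 patients from 33 clusters would have at least 80% power for all values of the ICC", for a 10-point difference with a standard deviation of 18.
- **Switch clock** (Study Design): each cluster moves to the video 2, 4 or 6 months after its own first patient. The delay is justified by the need for enough patients both before and after the video is introduced.
- **Design rationale** (Design of the PRIMETIME Information Giving Study): power is what the design is said to raise: "in a cluster stepped-wedge trial each cluster acts as its own control, increasing".

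**The concern.** A cluster receives the decision aid at its switch. All clusters have therefore received it when the last one switches, which is the start of that cluster's post-video period and not its end. The sample size counts patients from that later period; the trigger does not wait for them. The trigger depends on switch dates alone, and these follow automatically from each cluster's first patient, so it would be met whether or not 264 questionnaires had come back.

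At stake are the post-video data of the clusters that switch last, and hence their use as their own controls. The two secondary endpoints, acceptance of study entry and acceptance of recommended treatment, fall under the same final analysis.

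**Working it through.** **Inputs** (Appendix A5, Statistical Considerations): 33 clusters, 11 per step; switches at 2, 4 and 6 months; 2 patients per cluster per two-month period; difference 10; SD 18; alpha 0.05, taken as two-sided because sidedness is not stated.

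**1. Periods behind the target.** N = clusters × patients per period × periods.
- Four periods: 33 × 2 × 4 = 264, the plan's figure.
- Three periods: 33 × 2 × 3 = 198.
- Fallback: 30 × 2 × 4 = 240, also four periods.

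The fourth period, months 6 to 8 of each cluster's clock, is thus part of the design.

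**2. Reproducing the stated power.** The Hussey and Hughes variance of the effect, with I clusters, T periods, τ² = ICC × 18² and σ² = (1 − ICC) × 18²/2 for a cell mean of 2 patients, is

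Var = I σ²(σ² + Tτ²) / [(IU − W)σ² + (U² + ITU − TW − IV)τ²],

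where U is the number of exposed cluster-periods, W the sum of squared period totals and V the sum of squared cluster totals. Power = Φ(10/√Var − 1.96).

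- Four periods: U = 66, W = 1694, V = 154. IU − W = 484; second bracket = 1210. Power is 85.3% at ICC 0, with a minimum of 82.0% at ICC about 0.12. The claim of at least 80% at every ICC reproduces.
- Three periods: U = 33, W = 605, V = 55. IU − W = 484; second bracket = 726. Power is again 85.3% at ICC 0, with a minimum of 80.3% at ICC about 0.17.

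Example at ICC 0.17, three periods: σ² = 134.46, τ² = 55.08. Var = 33 × 134.46 × 299.70 / (484 × 134.46 + 726 × 55.08) = 12.66, so SE = 3.56 and power = Φ(2.81 − 1.96) = 80.3%.

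The largest loss at any ICC is about 4 percentage points. If the effect is taken as exactly 0.55 SD (9.9 points), the three-period minimum is 79.5%.

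**3. Data at the literal trigger, all clusters opening together.** 198 patients: 132 before and 66 after the video, against 132 and 132 planned. The 11 last-step clusters have none of their planned 11 × 2 = 22 post-video patients.

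**4. Data at the literal trigger, staggered opening.** Opening dates are not in the document. Assume uniform openings, and 1 patient per cluster per month (the planned rate). The trigger is the latest value of opening date plus switch time. Mean patients at the trigger, by simulation:

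| Opening spread | Clusters keep recruiting | Each cluster stops at 8 months |
|---|---|---|
| 0 months | 198 | 198 |
| 3 months | 239 | 236 |
| 6 months | 280 | 246 |
| 12 months | 364 | 252 |
| 24 months | 538 | 255 |

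At 6 months' spread without the stop, 86% of simulations reach 264, and last-step clusters average about 28 post-video patients against 22 planned. The stop at 8 months is a further assumption; the protocol sets no such closure.

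**5. Slower return (assumed rates), clusters opening together.** Power for ICC 0 to 0.3:

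| Patients per cluster-period | Three periods | Four periods |
|---|---|---|
| 1.5 | 149 patients, 70–74% | 198 patients, 72–76% |
| 1 | 99 patients, 55–58% | 132 patients, 56–60% |

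**The case against.** The strongest reply has four parts.

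- **Earliest time, not cut-off.** The sentence does not say that recruitment or questionnaire collection stops at the last switch, the target of 264 still stands, and the exact cut-off could be set in the statistical analysis plan, which is not shown. This has some force, but the protocol does state a rule. Its plain meaning is the last switch, and it mentions neither the target nor a post-switch period. A reader should not have to supply the condition.
- **Cluster-specific clocks.** A reader might infer that a quarter of the patients is always missing, or that last-step clusters as a group have little or no post-video data. The protocol does not support that. Each cluster is timed from its own first patient, so clusters that opened earlier can have completed their post-video period. Both statements hold only for simultaneous opening, and with a wide enough spread the trigger can come after 264. This part of the reply stands.
- **Power.** A reader might infer that the stated 80% is lost. At the planned rate and a 10-point difference it is not, even in the worst case. This stands too.
- **Slow return.** The 55–74% figures might be read as the price of the trigger. They are not: four full periods at the same rates give only 56–76%. They show only that the trigger takes no account of the data in hand.

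**Conclusion.** The trigger and the sample size in Appendix A5 disagree and should be reconciled. With the data cut at the literal trigger, the last cluster to switch has no post-video data under any opening pattern, against the stated aim of enough patients before and after the video.

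Beyond that one cluster, the shortfall ranges from 66 of 264 patients (25%) with simultaneous opening to none on average from about 6 months' spread. The latter assumes uniform openings and continued recruitment at the planned rate. The power loss is at most about 4 points, with a minimum of 80.3% against 82.0%, under the common-period model with two-sided alpha. Power under staggered opening was not computed. Severity is minor: the point concerns the embedded sub-study only and does not touch the main study.

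**What to change.** Replace the trigger sentence in Appendix A5, Statistical Analysis Plan, with one to this effect: the final analysis takes place when the last cluster has completed at least 2 months of recruitment after its switch to the decision aid and 264 questionnaires (or the fallback of 240) have been returned, whichever is later.

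The cost is one sentence and a delay of about 2 months to the sub-study's final analysis, longer if questionnaires return slowly. The main study is unchanged.
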